Section 8.11	

Study drug administration (after all predose assessments are completed) in the morning

 
The following procedures will be performed postdose:
 

Study drug administration 12h after the morning dose

	

Study drug administration (after all predose assessments are completed) in the morning 12h (<math>\pm 15\text{min}</math>) after the last dose

 
The following procedures will be performed postdose:
 

Study drug administration 12h (<math>\pm 15\text{min}</math>) after the morning dose

	Clarify assessment windows for vital signs and ECGs and for study drug administration
Section 8.12	

Study drug administration (after all predose assessments are completed) in the morning

 
The following procedures will be performed postdose:
 

Obtain vital sign measurements (BP and pulse rate) at 1, 2, and 4h postdose

Perform 12-lead ECGs at 1, 2, and 4h postdose

	

Study drug administration (after all predose assessments are completed) in the morning 12h (<math>\pm 15\text{min}</math>) after the last dose

 
The following procedures will be performed postdose:
 

Obtain vital sign measurements (SBP, DBP, pulse rate, respiratory rate, and body temperature<del>BP and pulse rate</del>) at 1, 2, and 4h postdose. A window of <math>\pm 15\text{min}</math> is allowed.

Perform 12-lead ECGs at 1, 2, and 4h postdose. A window of <math>\pm 15\text{min}</math> is allowed.

	Clarify assessment windows for vital signs and ECGs and for study drug administration
Section 8.15	

Obtain vital sign measurements (BP and pulse rate) at 72h postdose

Perform 12-lead ECG at 72h postdose

	

Obtain vital sign measurements (SBP, DBP, pulse rate, respiratory rate, and body temperature<del>BP and pulse rate</del>) at 72h (<math>\pm 15\text{min}</math>) postdose

Perform 12-lead ECG at 72h (<math>\pm 15\text{min}</math>) postdose

	Clarify assessment windows for vital signs and ECGs

Protocol section(s) impacted	Key components of previous protocol text	Key components of revised protocol text	Rationale
Change 13: Removed genotype analysis			
Section 9.2	
9.2 Genotype analysis
 
For the genotype analysis, 2.0mL of whole blood will be collected in a test tube containing ethylene diamine tetraacetic acid disodium salt (EDTA2Na). The sample will be sent to a genetic testing facility in a condition where individual identification is not impossible.
	
<del>9.2 Genotype analysis</del>
 
<del>For the genotype analysis, 2.0mL of whole blood will be collected in a test tube containing ethylene diamine tetraacetic acid disodium salt (EDTA2Na). The sample will be sent to a genetic testing facility in a condition where individual identification is not impossible.</del>
	Remove the genotype sample collection and analysis
Change 14: Removed the optional hepatic investigation sample collection			
Section 10.2.1.5	
10.2.1.5 Optional hepatic investigation sample collection
 
If a subject is undergoing further investigation for PDILI and has consented to retrospective genetic analysis per local regulations, the subject's blood sample will be shipped to a secure storage facility. The blood sample will be retained in the UCB Hepatic Investigation Biobank to solely support retrospective genetic analyses associated with an adverse therapeutic response to BRV.
 
Genetic analyses of deoxyribonucleic acid isolated from the blood will be contracted by UCB to specialized third-party laboratories and analysis will be limited to:
	
<del>10.2.1.5 Optional hepatic investigation sample collection</del>
 
<del>If a subject is undergoing further investigation for PDILI and has consented to retrospective genetic analysis per local regulations, the subject's blood sample will be shipped to a secure storage facility. The blood sample will be retained in the UCB Hepatic Investigation Biobank to solely support retrospective genetic analyses associated with an adverse therapeutic response to BRV.</del>
 
<del>Genetic analyses of deoxyribonucleic acid isolated from the blood will be contracted by UCB to specialized third-party laboratories and analysis will be limited to:</del>
 
 
• <del>Uridine 5' diphospho-glucuronosyltransferase loci – the loci</del>
 
	Remove the optional hepatic investigation sample collection

Protocol section(s) impacted	Key components of previous protocol text	Key components of revised protocol text	Rationale
	

• Uridine 5'-diphospho-glucuronosyltransferase loci – the loci responsible for Gilbert's syndrome (hyperbilirubinemia)

• Human leukocyte antigen (HLA) loci – for example, HLA-B5701 that has been associated with abacavir- and flucloxacillin-induced liver injury

• Absorption, distribution, metabolism, and excretion gene loci associated with abnormal pharmacokinetics

 
Genetic analysis of samples may be performed immediately, on a per-study basis, or as part of combined analyses across multiple studies belonging to the same clinical development program. As a result, samples will be retained for 15 years unless clinical development of the IMP is terminated, at which point all samples will be destroyed. The results determined using clinically approved diagnostic tests will be made available to the Investigator upon request.
 
Subjects may request at any time that their sample be removed from the UCB Hepatic Investigation Biobank and destroyed, though data from analyses already performed will remain on file. All samples, associated materials, and data will be kept securely by UCB and its agents. A sample destruction request should be made in writing to the Investigator who will notify the UCB Biorepository Manager (Global Exploratory Development, UCB, [name]).
	
responsible for Gilbert's syndrome (hyperbilirubinemia)
 
— Human leukocyte antigen (HLA) loci – for example, HLA-B5701 that has been associated with abacavir- and flucloxacillin-induced liver injury
 
— Absorption, distribution, metabolism, and excretion gene loci associated with abnormal pharmacokinetics
 
<del>Genetic analysis of samples may be performed immediately, on a per study basis, or as part of combined analyses across multiple studies belonging to the same clinical development program. As a result, samples will be retained for 15 years unless clinical development of the IMP is terminated, at which point all samples will be destroyed. The results determined using clinically approved diagnostic tests will be made available to the Investigator upon request.</del>
 
<del>Subjects may request at any time that their sample be removed from the UCB Hepatic Investigation Biobank and destroyed, though data from analyses already performed will remain on file. All samples, associated materials, and data will be kept securely by UCB and its agents. A sample destruction request should be made in writing to the Investigator who will notify the UCB Biorepository Manager (Global Exploratory Development, UCB, [name]).</del>
	

Protocol section(s) impacted	Key components of previous protocol text	Key components of revised protocol text	Rationale
		<del>Exploratory Development, UCB, [name]).</del>	
Change 15: Removed genotype analysis			
Section 12.3.1	If CYP2C19 poor metabolizers are identified in the study, data may also be summarized by CYP2C19 poor or extensive metabolizer status.	<del>If CYP2C19 poor metabolizers are identified in the study, data may also be summarized by CYP2C19 poor or extensive metabolizer status.</del>	Remove the genotype sample collection and analysis

## VERSION HISTORY

SAP Version	Approval Date	Change	Rationale
1.0	<24 May 2021>	Not Applicable	Original version
Amendment 1	<27 Aug 2021>	

1. Definition of ECG baseline (Section 5.6.3.3)

2. Summary tables of Urinalysis (Section 5.6.3.1.2)

3. Handling of BLQ values in individual concentration figures (Section 5.7.1.1)

	

1. To be consistent with the study protocol

2. To clarify the different summary tables for different data type of urinalysis and urine sediment forms

3. To comply with the UCB NCA data handling rules

## LIST OF ABBREVIATIONS

Ae	amount of drug excreted in the urine
AE	adverse event
AUC	area under the curve from 0 to infinite time
AUC (0-12),ss	area under the curve from 0 to 12 hours at steady state
AUC (0-t)	area under the plasma concentration-time curve from zero to the time of the last measured concentration above the limit of quantification
BLQ	below the limit of quantification
BMI	body mass index
BP	blood pressure
BRV	brivaracetam
C av,ss	average plasma concentration at steady state
CI	confidence interval
CL/F	apparent total body clearance
CL R	renal clearance
CL ss/F	apparent total body clearance at steady state
C max	maximum plasma concentration
C max,ss	maximum plasma concentration at steady state
C min,ss	minimum plasma concentration at steady state

---

CSR	clinical study report
CV	coefficient of variation
DEM	Data Evaluation Meeting
ECG	electrocardiogram
ES	Enrolled Set
fe	fraction of the dose excreted in the urine
IPD	Important protocol deviation
$\lambda_z$	rate constant of elimination
LLOQ	lower limit of quantification
MedDRA®	Medical Dictionary for Regulatory Activities
MRT	mean residence time
PCST	possibly clinically significant treatment-emergent
PD	pharmacodynamic
PK	pharmacokinetic
PK-PPS	Pharmacokinetic Per Protocol Set
PTF	peak trough fluctuation
R AUC	accumulation ratio calculated from AUC at steady state and AUC after single dose
R max	accumulation ratio calculated from C max at steady state and C max after single dose
SAE	serious adverse event
SAP	statistical analysis plan
SD	standard deviation
SFU	safety follow-up
SPD	Specification of Protocol Deviations
SS	Safety Set
t ½	terminal elimination half-life
TEAE	treatment-emergent adverse event
t max	time to reach maximum plasma concentration
Vz/F	apparent volume of distribution
WHO-DRL	World Health Organization Drug Reference List

This document cannot be used to support any marketing authorization application and any extensions or variations thereof.

## 1 INTRODUCTION

This statistical analysis plan (SAP) defines the scope of statistical analyses and provides a detailed description of statistical methodology for the statistical analyses to support the final clinical study report (CSR) for study EP0101. The SAP is based on the following study document: Protocol Amendment 2, 08 Jan 2021.

### 1.1 Objectives and Endpoints

**Table 1-1: Objectives and Endpoints**

Objectives	Endpoints
To assess the pharmacokinetics (PK), safety, and tolerability of BRV after a single dose and multiple doses of 100mg for 6 days in healthy adult Chinese participants (male and female).	
Primary PK Endpoints:
 

• Concentrations of BRV and 3 metabolites (ucb-42145, ucb-100406-1, and ucb107092-1) in plasma

• For the single dose:

◦ <math>AUC_{(0-t)}</math> of BRV

◦ <math>C_{max}</math> of BRV

• For the multiple dose:

◦ <math>AUC_{(0-12),ss}</math> of BRV

◦ <math>C_{max,ss}</math> of BRV

 
Secondary PK Endpoints:
 

• For the single dose:

◦ <math>t_{max}</math>, <math>t_{1/2}</math>, <math>\lambda_z</math>, MRT, AUC, CL/F, and <math>V_z/F</math> of BRV in plasma

◦ <math>C_{max}</math>, <math>t_{max}</math>, <math>t_{1/2}</math>, <math>\lambda_z</math>, <math>AUC_{(0-t)}</math>, and AUC of metabolites in plasma

• For the multiple dose:

◦ <math>t_{max}</math>, <math>t_{1/2}</math>, <math>\lambda_z</math>, <math>C_{min,ss}</math>, <math>C_{av,ss}</math>, <math>CL_{ss}/F</math>, and <math>V_z/F</math> of BRV in plasma

◦ <math>t_{max}</math>, <math>t_{1/2}</math>, <math>\lambda_z</math>, <math>C_{max,ss}</math>, and <math>AUC_{(0-12),ss}</math> of metabolites in plasma

◦ PTF of BRV in steady-state

◦ <math>R_{AUC}</math> and <math>R_{max}</math> of BRV

**Table 1–1: Objectives and Endpoints**

Objectives	Endpoints
	
Primary Safety Endpoints:
 
 
• Incidence of treatment-emergent AEs (TEAEs)
 
 
Other Safety Endpoints:
 
 
• Changes in vital signs (SBP, DBP, pulse rate, respiratory rate, and body temperature)
 
• Standard 12-lead ECGs parameters and findings
 
• Changes in clinical laboratory test parameters (hematology, blood chemistry, and urinalysis)
 

## 1.2 Study design

This is a Phase 1, single site, open-label, single and multiple dose PK study of BRV tablets in healthy male and female Chinese participants. Participants are confined to the clinical trial unit from Day -1 (the day prior to first administration of BRV) until Day 13.

A total of 12 participants (6 males and 6 females) who have signed the informed consent form and fulfilled all inclusion and none of the exclusion criteria are planned to be enrolled and will start the Single-Dose Period. In the Single-Dose Period, each subject receives a single dose of BRV 100mg. In the Multiple-Dose Period, the multiple-dose PK and safety of BRV 200mg/day (100 mg every 12h  $\pm$  15 min) are evaluated in the same participants as in the Single-Dose Period.

In the Single-Dose Period, participants will receive a single dose of BRV under fasting conditions with 200mL water. Blood samples will be taken for the determination of the PK profile of BRV and its metabolites (ucb-42145, ucb-100406-1, and ucb107092-1) at predose, and 0.25, 0.5, 1, 1.5, 2, 3, 4, 6, 9, 12, 16, 24, 36, 48, and 72h after investigational medicinal product (IMP) administration (Table 1–2).

**Table 1–2: Single-Dose Period: schedule for ECGs, vital signs, and PK sampling**

Assessment	Time relative to BRV administration															
			Postdose (h)													
	Day 1												Day 2			
	Predose	0.25	0.5	1	1.5	2	3	4	6	9	12	16	24	36	48	72
12-lead ECG	X a	--	--	X	--	X	--	X	--	--	--	--	--	--	--	X
Vital signs b	X	--	--	X	--	X	--	X	--	--	--	--	--	--	--	X
Blood samples for PK	X	X	X	X	X	X	X	X	X	X	X	X	X	X	X	X

BRV=brivaracetam; DBP=diastolic blood pressure; ECG=electrocardiogram; PK=pharmacokinetics; SBP=systolic blood pressure  
 a. Three ECGs to be performed at 15min ( $\pm$ 5min) intervals within 24h prior to BRV dosing on Day 1 to provide a representative baseline  
 b. Vital sign assessments include SBP, DBP, pulse rate, respiratory rate, and body temperature.

In the Multiple-Dose Period, participants will receive BRV 200mg/day (100mg every 12h  $\pm$ 15min). Participants will receive BRV under fasting conditions with 200mL water. Blood samples will be taken for the determination of the PK profile of BRV and its metabolites (ucb-42145, ucb-100406-1, and ucb107092-1) predose prior to the morning dose administration on Day 5 to Day 9, and at predosing and at the following time points after the last administration of the IMP on Day 10: 0.25, 0.5, 1, 1.5, 2, 3, 4, 6, 9, 12, 16, 24, 36, 48, and 72h (Table 1–3).

**Table 1–3: Multiple-Dose Period: schedule for ECGs, vital signs, and PK sampling**

Assessment	Day																				
	5	6	7	8	9	10							11	12	13						
	Pre	Pre	Pre	Pre	Pre	Pre	Postdose (h)														
							0.25	0.5	1	1.5	2	3	4	6	9	12	16	24	36	48	72
12-lead ECG	--	--	X a	--	--	X	--	--	X	--	X	--	X	--	--	--	--	--	--	--	X
Vital signs b	--	--	X a	--	--	X	--	--	X	--	X	--	X	--	--	--	--	--	--	--	X
Blood samples for PK	X c	X	X	X	X	X	X	X	X	X	X	X	X	X	X	X					

DBP=diastolic blood pressure; ECG=electrocardiogram; Pre=predose; SBP=systolic blood pressure

aTo be performed predose on the morning of Day 7.

bVital sign assessments include SBP, DBP, pulse rate, respiratory rate, and body temperature

cTo be collected predose in the morning.

Participants will be discharged from confinement in the morning of Day 13, approximately 72h after the final administration of IMP, provided there are no medical objections.

Safety and tolerability of BRV will be assessed throughout the study by monitoring of AEs, collecting blood and urine samples for the evaluation of safety laboratory parameters, measuring vital signs (SBP, DBP, pulse rate, respiratory rate, and body temperature), and ECG.

A Safety Follow-up (SFU) Visit will be performed after the final administration of the IMP. The assessments performed for the SFU will also be performed for early withdrawals.

The anticipated maximum study duration per participant is 43 days (approximately 6 weeks), including the Screening Period (up to 28 days), confinement during the Single-Dose and Multiple-Dose Periods (13 days), and follow-up examination (2 days after clinic discharge).

The end of the study is defined as the date of the final visit of the final participant in the study.

## 2 STATISTICAL HYPOTHESES

No statistical comparisons with hypothetical inference are planned for the primary analysis of the pharmacokinetic variables.

### **3 SAMPLE SIZE DETERMINATION**

A total of 12 healthy (6 male and 6 female) participants is planned to be enrolled at one site in China and allocated to the treatment.

Due to the primary objective of the study being related to PK and safety, no power calculation of the study sample size is performed.

### **4 POPULATIONS FOR ANALYSIS**

PK variables are summarized using the Pharmacokinetic Per-Protocol Set (PK-PPS), and safety variables are summarized using the Safety Set (SS).

Subject data listings are prepared for participants with available data (Enrolled Set [ES], SS, or PK-PPS), depending on the domain.

The reasons for exclusion of participants from either of the analysis sets will be listed.

#### **4.1 Enrolled Set**

The ES consists of all participants who gave informed consent including screen failures. This analysis set is also referred to as “All Participants Screened.”

#### **4.2 Safety Set**

The SS consists of all participants who received at least 1 dose of IMP.

#### **4.3 Pharmacokinetic Per-Protocol Set**

The PK-PPS consists of all participants who are included in the SS and also have a sufficient number of bioanalytical assessments to calculate reliable estimates for the primary PK parameters.

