#### **5.1.1.2      Protocol Deviations**

Important protocol deviations (IPDs) are deviations from the protocol which potentially could have a meaningful impact on the key safety or PK outcomes or on study conduct for an individual subject.

The criteria for identifying important protocol deviations and the classification of important protocol deviations are defined within the protocol-specific document, Specification of Protocol Deviations (SPD). To the extent feasible, rules for identifying protocol deviations are defined without review of the data and without consideration of the frequency of occurrence of such deviations. They are identified from various sources such as programmed edit checks, programmed listings, and monitoring reports, and finalized in the SPD during the Data Evaluation Meeting (DEM) prior to database lock.

Any samples that are obtained outside the tolerance window permitted at the specified timepoint will be discussed at the DEM and any possible exclusion from analysis will be documented accordingly.

The categories (eg, inclusion/exclusion criteria, withdrawal criteria, Prohibited concomitant medication use, treatment/procedure non compliance, and incorrect treatment or dose) are not fixed and can be adapted, extended, or reduced according to the needs of the study.

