### **Primary/secondary pharmacokinetic parameters**

Plasma pharmacokinetic parameters as identified above are calculated from the individual drug concentration vs. actual time profiles by dosing period. Parameters are calculated for BRV and metabolites after single and multiple dose as described in **Table 5-4**.  

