#### PK parameters in plasma

- AUC parameters (AUC(0-t), AUC(0-12), AUC(0-12),ss, AUC) [ng·h/mL]
  - The linear up/log down trapezoidal method is used to calculate the AUC parameters.
  - AUC: Calculated as AUC(0-t)+Clast/λz
    - If the percentage of extrapolated AUC (AUCextr) is more than 20%, the individual result should be excluded from summary statistics along with all parameters dependent on AUC.
- Cmax parameters (Cmax, Cmax,ss) [ng/mL]
  - Obtained directly from the concentration vs. time data

- $C_{\min,ss}$  [ng/mL]
  - Obtained directly from the concentration vs. time data
- $C_{av,ss}$  [ng/mL]
  - Calculated as  $AUC_{(0-12),ss}/12$
- $t_{\max}$  [h]
  - Obtained directly from the concentration vs. time data as a time at which  $C_{\max}$  or  $C_{\max,ss}$  is observed.
- $\lambda_z$  [1/h]
  - Estimated at terminal phase by linear regression after natural log-transformation of the concentrations.  $\lambda_z$  is calculated over a time interval using the best fit method.
    - The time interval should be equal to at least  $2 \times t_{1/2}$  and have at least 3 data-points not including  $C_{\max}$ . If it is less than 2 half-lives or if there are too few data to calculate  $\lambda_z$ , then the parameter should be excluded from summary statistics (along with all parameters dependent on half-life).
    - In the case that the  $R^2$  for the regression is less than 0.8, the half-life (and all parameters dependent on it) should be excluded from summary statistics.
  - Calculated as  $\ln 2 / \lambda_z$ 
    - For the parameter, same notation as corresponding  $\lambda_z$  is noted in the listing if the  $\lambda_z$  has the above-mentioned notation.
- MRT [h]
  - Calculated after single dose as  $AUMC/AUC$ , where AUMC is the area under the first moment curve from 0 to infinite time
  - $AUMC = AUMC_{(0-t)} + C_{\text{last}} \times t_{\text{last}} / \lambda_z + C_{\text{last}} / \lambda_z^2$
  - $AUMC_{(0-t)} = \int_0^{t_{\text{last}}} C(t) \times t \, dt$
- CL/F [L/h]
  - Calculated as dose/AUC
- $CL_{ss}/F$  [L/h]
  - Calculated as dose/ $AUC_{(0-12),ss}$
- $V_z/F$  [L]
  - Calculated as  $CL/F/\lambda_z$
- PTF
  - Calculated as  $(C_{\max,ss} - C_{\min,ss})/C_{av,ss}$

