### 6.1.2 Protocol deviations

The number and percentage of participants with at least 1 IPD are summarized for SS, using the categories as defined in the protocol deviation specification.

A listing of all IPDs identified at the DEM will be presented based on the SS and will include the deviation type and description.

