#### **6.1.7        Compliance**

A study participant is considered compliant with treatment if the participant takes the study IMP at all of 12 scheduled time points. Participants who do not take all 12 doses are to be considered non-compliant to treatment and are to be discussed at the DEM. A data listing for treatment compliance is not provided.

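### Does the PK Per-Protocol Set need a written rule for missed or incorrect doses?

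*SAP*

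**What the plan says.** SAP 4.3 and Protocol 12.1 define the PK-PPS identically: Safety Set participants who "also have a sufficient number of bioanalytical assessments to calculate reliable estimates for the primary PK parameters". Neither sets a dosing or compliance condition.

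Dosing deviations are handled elsewhere:

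- SAP 5.1.1.2 counts "treatment/procedure non compliance, and incorrect treatment or dose" among the deviation categories. The criteria sit in the Specification of Protocol Deviations (SPD) and are finalized at the DEM before lock. It adds: "To the extent feasible, rules for identifying protocol deviations are defined without review of the data".
- SAP 6.1.7: "Participants who do not take all 12 doses are to be considered non-compliant to treatment and are to be discussed at the DEM".
- SAP 6.1.2: "A listing of all IPDs identified at the DEM will be presented based on the SS". A count by category is also planned.
- SAP 4 requires the reasons for exclusion from an analysis set to be listed.
- Protocol 6.3 says subjects should be withdrawn if the investigator judges them noncompliant with medication, or if a deviation may markedly affect results.

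Exclusion from analysis is mentioned in two places. Samples outside the time window "will be discussed at the DEM and any possible exclusion from analysis will be documented accordingly" (SAP 5.1.1.2). SAP 5.7.1.1 sets numeric reliability rules; for example, when more than 20% of AUC is extrapolated, "the individual result should be excluded from summary statistics along with all parameters dependent on AUC".

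**The concern.** The set is called per-protocol, yet a dosing failure does not remove anyone from it on the written definition. The only sentence that ties DEM review to exclusion concerns sampling times, and parameters "are calculated from the individual drug concentration vs. actual time profiles by dosing period", so a late sample hardly changes them. The numeric rules in SAP 5.7.1.1 (extrapolation above 20%, R² below 0.8, fewer than two half-lives) act on AUC to infinity, the terminal slope and their dependents. None acts on AUC(0-t), Cmax, AUC(0-12),ss or Cmax,ss. The not-calculable flag does not help either, because a fully sampled profile after a missed dose calculates without difficulty. The set is also defined once per participant, while results are summarized by dosing period.

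At stake are the geometric mean, confidence interval and CV of the multiple-dose primary parameters, and the accumulation ratios. In an open-label study, keeping or dropping a low profile case by case, perhaps with the concentrations in view, is what a per-protocol definition should prevent.

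**Working it through.** **Inputs.** Half-life about 9 h (Protocol 1 and 2). Dosing interval 12 h; n = 12. Clearance 0.70 against 0.99 mL/min/kg in subjects with two nonfunctional CYP2C19 alleles (Protocol 1), which gives a longer half-life of 9 × 0.99/0.70 = 12.7 h if volume is unchanged (assumed). Also assumed: linear one-compartment kinetics, ka 1.5 to 6 per hour, between-subject CV 20%.

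**The plan's own figure.** Doses per participant: 1 (Day 1) + 2 × 5 (Days 5 to 9) + 1 (Day 10) = 12. This matches SAP 6.1.7.

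**Effect of one missed dose on that participant.** With k = ln 2/9 = 0.0770 per hour, r = exp(-12k) = 0.397. Treating absorption as instantaneous, the dose given m intervals before the Day 10 dose contributes (1 - r) × r^m of AUC(0-12),ss. For m = 1 this is 0.603 × 0.397 = 23.9%. The other columns add first-order absorption, the planned sampling times and the SAP's linear-up/log-down rule.

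| Missed dose | Formula, 9 h | Sampled profile, 9 h | Sampled profile, 12.7 h |
|---|---|---|---|
| Day 9 evening | -23.9% | -24.3 to -25.3% | -25.3 to -26.0% |
| Day 9 morning | -9.5% | -9.7 to -10.0% | -13.1 to -13.5% |
| Day 8 evening | -3.8% | -3.8 to -4.0% | -6.8 to -7.0% |
| Day 8 morning | -1.5% | -1.5 to -1.6% | -3.6 to -3.7% |

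For the Day 9 evening dose at 9 h, Cmax,ss falls 24.6 to 24.8% and the Day 10 predose value falls 60.3%. The AUC accumulation ratio drops from 1.68-1.72 to 1.27-1.29. If the Day 10 dose itself were missed and every sample still drawn, AUC(0-12),ss would be about 60% low (m = 0: 1 - r = 0.603).

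**Effect on the summary of 12.**

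- Day 9 evening dose missed in one participant: 0.747^(1/12) - 1 = -2.4%.
- Day 10 dose missed in one participant: 0.397^(1/12) - 1 = -7.4%.
- Confidence interval at 20% CV: the log-scale SD is √ln(1 + 0.20²) = 0.198 and t on 11 degrees of freedom is 2.201. Half-width 2.201 × 0.198/√12 = 0.126, so the limits are exp(±0.126) = 0.882 to 1.134, or about -12% to +13%.
- One Day 9 evening miss raises a 20% geometric CV to about 21.6%.

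**Late or early samples, for comparison.** One Day 10 sample displaced by five times its window, with actual times used, moves AUC(0-12),ss by at most 0.15% and Cmax,ss by at most 1.3%. Plasma concentrations are also a primary variable, however, and are summarized by scheduled time. After a single dose, concentration is proportional to exp(-kt) - exp(-ka·t). Drawing the 0.25 h sample 5 minutes late raises it by:

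- ka 1.5: 0.368/0.294 = 1.25, or +25%;
- ka 6: 0.839/0.758 = 1.11, or +11%.

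Drawn 5 minutes early, it is 18 to 29% low. The sentence on out-of-window samples therefore has a real use.

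**The case for a change.** The strongest argument for a change is that the effect can be calculated in advance. The schedule is fixed, carry-over fades in a known way, and SAP 5.1.1.2 favours rules set without sight of the data. Two analysts following SAP 4.3 and 6.1.7 could report different n, geometric mean and CV. The deviation with no stated consequence moves one participant's primary parameter by a quarter. All of this is correct as a description of the text, and the size for the individual profile stands.

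It does not carry through to a needed change:

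- The sentence on advance rules concerns identifying deviations. The plan assigns that to the SPD, which is not public and may already hold dosing criteria.
- Missed doses cannot pass unnoticed. Administration is supervised and timed in the eCRF (Protocol 7.7), in confinement (Protocol 8.2), and every shortfall from 12 is discussed before lock.
- A participant withdrawn under Protocol 6.3 before Day 10 has no Day 10 profile and fails the sample-number test. Protocol 12.6 replaces dropouts for reasons other than safety.
- The 60% case is hardly credible in practice. Without a Day 10 dose, the scheduled postdose times have no dose to run from.
- A fixed limit is hard to draw well. How many preceding doses must be intact depends on the half-life. A time limit for vomiting depends on ka: the unabsorbed fraction, exp(-ka·t), is 0.2 to 22% at 1 h and at most 5% at 2 h under the assumed range. A strict cut could discard nearly intact profiles from a set of 12.

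**Conclusion.** The gap in SAP 4.3 is real, but it is missing detail that the planned process fills. A missed dose is recorded, sent to the DEM and decided before lock. Any exclusion is listed with its reason, and individual parameters are listed for the Safety Set, so a reader can recompute the summary with or without the profile. Taking membership by dosing period is the natural reading, since SAP 5.7.1.1 summarizes by period and applies its two-thirds rule parameter by parameter.

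If the meeting kept one profile after a missed Day 9 evening dose, the geometric mean would shift by about -2.4%, well inside an interval of about -12% to +13%. SAP 2 plans no hypothesis test that this could affect. These sizes rest on the 9 h half-life from the documents and on assumed linear one-compartment kinetics, ka of 1.5 to 6 per hour and a 20% CV. The longer half-life changes the individual effect only to about 25-26%. What the documents cannot show is the content of the SPD, or whether concentrations will be visible at the DEM. No change to the plan follows.
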